GCS Co., Ltd.	GANA V [®]	Final version 5.0	Confidential
	CIP #21E0787	Date: 27/06/2022	Page 1/6

OVERALL SYNOPSIS OF THE CLINICAL INVESTIGATION # 21E0787

ANSM registration #:	2021-A02451-40				
Clinical investigation plan #:	21E0787				
Title of the clinical investigation:	Clinical study for the safety and effectiveness of use of an injectable medical device GANA $V^{\mbox{\tiny B}}$ for facial aesthetic treatment				
Sponsor:	GCS Co., Ltd. [name]				
Development phase	Post market study Interventional Device used according to Instruction For Use (IFU)				
Objectives:	 The primary objective is to evaluate the effectiveness of Gana V[®] in comparison with Sculptra[®] in the correction of Nasolabial Folds (NLFs) 6 months after treatment initiation. The secondary objectives of the study are: To evaluate the effectiveness of Gana V[®] in comparison with Sculptra[®] in the correction of Nasolabial Folds (NLFs) 1^{1/2}, 3, 9, 12, 18 and 24 months after treatment initiation. To evaluate the effectiveness of Gana V[®] in comparison with Sculptra[®] on the global aesthetic improvement 1^{1/2}, 3, 6, 9, 12, 18 and 24 months after treatment initiation. To evaluate the effectiveness of Gana V[®] in comparison with Sculptra[®] on the global aesthetic improvement 1^{1/2}, 3, 6, 9, 12, 18 and 24 months after treatment initiation. To evaluate the effectiveness of Gana V[®] in comparison with Sculptra[®] in reducing NLFs depth and volume 1^{1/2}, 3, 6, 9, 12, 18 and 24 months after treatment initiation. To evaluate the subject satisfaction with Gana V[®] in comparison with Sculptra[®] 1^{1/2}, 3, 6, 9, 12, 18 and 24 months after treatment initiation. To evaluate the injector satisfaction with Gana V[®] in comparison with Sculptra[®] 1^{1/2}, 3, 6, 9, 12, 18 and 24 months after treatment initiation. To evaluate the injector satisfaction with Gana V[®] in comparison with Sculptra[®] after initial injection and touch-up injection if applicable. To evaluate the safety of Gana V[®] in comparison with Sculptra[®]. 				
Design:	 The study will be: double-blinded, randomized, within-subjects: each subject testing both devices, versus comparator, single centre. 				
Planned Sample Size:	55 subjects randomized.				
Number of investigational study sites:	1 site (France)				

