Inclusion criteria:	 Healthy Subject Sex: male or female Age: between 30 and 70 years. Subject with moderate to severe nasolabial folds as determined by a Wrinkle Severity Rating Scale (WSRS) score of 3 or 4 on both folds at the pre-treatment evaluation. 				

GCS Co., Ltd.	GANA V [®] CIP #21E0787	Final version 5.0 Date: 27/06/2022	Confidential Page 2/6
	fillers, to peels, n period. 6. Subject, informati 7. Subject consent. 8. Subject v 9. Subject a 10. Female regimen	xin treatments, laser, micr on-invasive skin-tightening psychologically able to ur on and to give a written info having given freely and willing to have photographs affiliated to a health social s of childbearing potential s	expressly his/her informed of the face taken. ecurity system. should use a contraceptive ice at least 12 weeks before
Exclusion criteria:	 study. 2. Subject with face of the f	with a scar, moles, pigmen which might interfere with the who had been deprive rative or legal decision or w in a social or sanitary estable participation to another res an exclusion period of one having received 4500 tion in research involving months, including participal suspected to be non-co tor's judgment. suffering from a severe or p thology that may interfere sults.	ed of their freedom by ho is under guardianship. lishment earch on human beings or euros indemnities for human beings in the 12 tion in the present study. mpliant according to the progressive disease or any with the evaluation of the

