Study Procedures:	CIP #21E0787 "Imp acco - Meat 3, 6, fring - Prop mon - Injec and Secondary s Investigation Injection Site the study by their subject A screening On D0, base photographs receive a firs randomizatio satisfaction Adverse Ev immediately A month and scoring, fring before touch injector's tre touch-up inje subject opin before and a	Date: 27/06/2022 roved", "Much improved" or ording to GAIS. In change in NLF depth and 9, 12, 18 and 24 months at e projection system. Nortion of satisfied subjects ths after treatment initiation stor's satisfaction regarding touch-up injection using a q afety endpoints: al devices safety will be Reactions (ISRs) and Adve the investigator. Subjects diaries. visit will allow to inform and eline scoring (WSRS), fringe will be done before inje t injection of the investigation on list. Immediately after in will be collected. Investig rents (AEs) and Injection after injection. d a half after initial injection ge projection acquisitions ar -up (if applicable). Subject' atment satisfaction (if app ction will be made if necessa- ion. Investigator evaluator fter touch-up if applicable.	"Very much improved" score volume from baseline to 1 ^{1/2} , fter treatment initiation using 1 ^{1/2} , 3, 6, 9, 12, 18 and 24 using a questionnaire. injection quality after initial questionnaire. assessed by collection of erse Events (AEs) throughout will record ISRs and AEs in preselect the subjects. e projection acquisitions and ction. Eligible subjects will onal devices according to the njection, injector's treatment gator evaluator will collect on Site Reactions (ISRs) n (M1 ^{1/2}), WSRS and GAIS nd photographs will be done s treatment satisfaction and licable) will be collected. A ary, according to injector and will collect AEs and ISRs
	twenty-four((WSRS and photographs	M24) months after initial inju I GAIS scales), fringe p	(M12), eighteen (M18) and ection, effectiveness scoring projection acquisitions and eatment satisfaction will be ect AEs and ISRs
Otatiatia - Love the L		nary evaluation criterion:	
Statistical methods:	The parame level scores (statistics for deviation, firs	ter Wrinkle Severity Rating (at D0 before injection and N quantitative variable (N, st and third quartile, minimu	g Scale (WSRS) with the 5 /6) will be summarized using , mean, median, standard um and maximum value) for le from baseline (M6-D0bef)
	Inferential a	nalysis for the primary en	idpoint:

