	if the upper-		culptra [®] will be demonstrated CI of the (M6-D0bef) mean
	For the seco	ondary evaluation criteria:	.
	All the variab to their type For quantitat	oles will be described using (quantitative data or qualitat	adapted statistics according tive data). ired t test will be applied to

GCS Co., Ltd.	GANA V [®] CIP #21E0787		Final version 5.0 Date: 27/06/2022	Confidential Page 5/6
For qualitative data a McNemar's test will be applied t proportion of improvement or satisfaction between the The bilateral approach will be used with a significance				n between the products.
Foreseen study duration:		Clinical inves Clinical inves	tigation beginning: Q1 202 tigation end: Q2 2024 tigation global duration: 28 ubject: 24 months + screer	months

GCS Co I th	idential ge 6/6
-------------	--------------------

FLOW-CHART							1		
Procedure	Visit 1 Screenin g	Visit 2 Day 0	Visit 3 M1 ^{1/2}	Visit 4 M3	Visit 5 M6	Visit 6 M9	Visit 7 M12	Visit 8 M18	Visit 9 M24
Days	D-x	D0	D40 ±2	D90 ±2	D180 ±4	D270 ±4	D365 ±7	D540 ±14	D730 ±14
Informed consent form signature	•								
Medical examination	•								
Medical history and previous and concomitant treatments collection	•								
Checking of the inclusion and exclusion criteria	•								
Pregnancy test		●b							
Confirmation of eligibility		●b							
Randomization		•							
WSRS live assessment by a blinded evaluator	•	●b	●b	•	•	•	•	•	•
Macrophotographs		●b	●b	•	•	•	•	•	•
Fringe projection acquisitions (2 areas)		●b	●b	•	•	•	•	•	•
Injection + anaesthesia (if necessary)		•	Touch up						
GAIS live assessment by a blinded evaluator			●b	•	•	•	•	•	•
GAIS assessment by the subjects			●b	•	•	•	•	•	•
Subjective evaluation questionnaire for subjects			●b	•	•	•	•	•	•
ISR assessor		●a	●b+a	•	•	•	•	•	•
ISR subjects		completed each day during 4 weeks after injection and touch up if applicable at home by the subject							
Subjective evaluation questionnaire for injector		●a	●a						
AE and concomitant treatments and procedures collection	•	•	•	•	•	•	•	•	•
Study end									•

Keys:^b: Before injection; ^a: After injection

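### NLF depth and volume: estimating the slope on the D0 fold difference, rather than only subtracting D0, could narrow the confidence intervals at little cost (precision only; the planned paired t test is valid)

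*Combined protocol and SAP*

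**What the plan says.** - **Design and Planned Sample Size:** a within-subject comparison in which each subject receives both devices; 55 subjects are randomized.
- **Objectives:** Gana V is compared with Sculptra "in reducing NLFs depth and volume" at seven times, from 1½ to 24 months.
- **Endpoints:** the secondary endpoint ("In change in NLF depth and" volume) is a change from baseline measured by fringe projection.
- **Flow-chart:** "Fringe projection acquisitions (2 areas") and "WSRS live assessment by a blinded evaluator" are both marked at D0 before injection and at every follow-up visit.
- **Statistical methods, secondary criteria:** quantitative data get a paired t test ("ired t test will be applied to"). The object of that sentence is lost.
- **Statistical methods, primary criterion:** WSRS is summarized as a change ("le from baseline (M6-D0bef") and judged by the upper limit of a "CI of the (M6-D0bef) mean". The margin and confidence level are not legible.
- **Inclusion criteria:** a WSRS "score of 3 or 4 on both folds at the pre-treatment evaluation". No legible rule requires the two folds to have the same score.

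No legible sentence mentions a baseline covariate or a regression model. The document is a synopsis and its statistical section is cut, so this describes the legible text and does not establish that the plan has no adjustment.

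**The concern.** A paired t test on change compares the two folds after taking the whole D0 difference off the follow-up difference. That is the most precise choice only if a D0 difference of one unit carries forward, on average, as one unit. If part of the D0 difference is measurement error, or fades over time, the true slope is below 1. Subtraction then over-corrects and leaves avoidable variance in the contrast.

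The stake is the width of the confidence intervals for depth and volume at seven visits with 55 subjects. The D0 values are already being collected, so any gain needs no further data. Bias is not at stake.

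**Working it through.** **Set-up.** For each subject let X be the D0 fold difference and Y the follow-up fold difference, both Gana V minus Sculptra. Write Y = a + bX + e, with residual SD s. With product randomized to fold, X has mean zero and a is the treatment contrast.

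- Planned analysis: the mean of Y − X, with variance per subject s² + (1−b)²·Var(X).
- Adjusted analysis: the intercept a, with variance per subject s², inflated slightly because b is estimated.

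Let k = SD(X)/s. The ratio of CI widths, adjusted over planned, is about

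C / √(1 + (1−b)²k²), where C = √(1 + 1/52) × t(0.975, 53)/t(0.975, 54) = 1.010 for n = 55.

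**Inputs.** From the documents: n = 55 (randomized), the paired design, and D0 measurement before injection. Assumed: two-sided 95% intervals, all 55 analysed, and b and k over a range. No SD, correlation, margin or power is legible, so the planned sample size cannot be reproduced and there is no plan figure to match.

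**Depth and volume, CI width ratio:**

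| Slope b | k = 0.25 | k = 0.5 | k = 1 | k = 1.5 |
|---|---|---|---|---|
| 0.5 | 1.002 | 0.980 | 0.903 | 0.808 |
| 0.8 | 1.009 | 1.005 | 0.990 | 0.967 |
| 1 | 1.010 | 1.010 | 1.010 | 1.010 |

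Example: for b = 0.5 and k = 1, 1.010/√(1 + 0.25) = 0.903. In sample-size terms, 1/0.903² = 1.23, or about 23% more subjects. Break-even is at (1−b)k = √(1.010² − 1) = 0.142. Simulated means agree with the formula within 0.003. At slope 1 the adjusted interval is at least about 4% wider in 5% of runs and at least about 7% wider in 1%.

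**Second parameterization.** If the D0 and follow-up fold differences have equal SDs and correlation ρ, the standard-error ratio is √((1+ρ)/2). Simulated CI width ratios (10,000 runs) were 0.78, 0.82, 0.87, 0.93 and 0.98 for ρ = 0.2, 0.3, 0.5, 0.7 and 0.9. Both estimators were unbiased, with coverage near 95%.

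**WSRS, for comparison.** With both folds at 3 or 4, X can only be −1, 0 or +1. A simulation used integer scores, n = 55 and a fold-difference error SD of 0.6 before rounding (residual SD about 0.72 after rounding). Mean width ratios by share of subjects with unequal D0 folds:

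| Slope b | 5% | 10% | 20% | 30% | 50% |
|---|---|---|---|---|---|
| 0.5 | 0.998 | 0.987 | 0.966 | 0.946 | 0.908 |
| 0.8 | 1.007 | 1.006 | 1.002 | 0.998 | 0.991 |
| 1 | 1.009 | 1.010 | 1.010 | 1.010 | 1.010 |

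With scores of 3 or 4 and equal marginals, the unequal share is at most 0.5(1−r), where r is the between-fold correlation. A share of 30% needs r of 0.4 or less; 10% is possible with r up to 0.8. The lower shares are therefore more plausible. At 10% and slope 0.5 the mean gain is about 1%, and the adjusted interval is the wider one in 42% of runs.

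**The case against.** The strongest reply is that nothing here is wrong. The endpoints are defined as changes from baseline, a paired t test on change suits them, and preferring a regression is a refinement. This stands: the point is an improvement, and a reader who infers bias or invalidity goes beyond the documents.

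Second, the statistical text is cut. The sentence on the paired t test has lost its object, so even the use of change scores there is inferred from the endpoint definitions. The full plan may already adjust. This also stands, and it makes the recommendation conditional.

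Third, slope and SD ratio are assumed, and the range includes a small loss. True, but the two sides are unequal: an average loss of about 1% against a gain that reaches 10% to 19% where the slope is 0.5 and the folds differ appreciably at D0.

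A reader might also infer that the primary M6 WSRS analysis should be changed in the same way, perhaps once some number of subjects prove to have unequal folds. The documents do not support that. The primary rule is cut, and at unequal shares of 5% to 10% the expected effect runs from a gain of about 1% to a loss of about 1%. A cut-off would also rest on an undocumented SD: at 10% unequal and slope 0.5, the gain is about 1% with a pre-rounding SD of 0.6 but about 3% with 0.4. Amending a primary estimator after the planned start is not justified by this.

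**Conclusion.** The point holds for NLF depth and volume as a matter of precision only, with medium confidence. The size depends on the slope and on how much the folds differ at D0 relative to residual noise, and the documents give neither. It also assumes that the randomization list assigns product to fold and that the two fringe-projection areas are the two folds. It does not extend to GAIS or the satisfaction questionnaires, which have no D0 value.

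No margin or SD is legible, so it cannot be inferred that adjustment would change what the trial concludes.

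**What to change.** Unless the full text already adjusts, add the following for depth and for volume at each follow-up visit: regress the within-subject follow-up difference (Gana V minus Sculptra) on the within-subject D0 difference, and report the intercept with its CI. Keep the paired t test on change as the sensitivity analysis. The same model may be used for WSRS change at the secondary visits, reverting to the raw paired difference if no subject has unequal folds. Leave the primary estimator unchanged.

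The cost is one sentence in the analysis plan, one model term and one degree of freedom, with no new data. Version 5.0 is dated 27/06/2022, and a Q2 2024 end less 28 months puts the planned start around Q1 2022. The change would therefore come after the planned start and must be fixed before unblinding.

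### The paired t test for quantitative secondary endpoints shows no term for allocated side; adding one is a cheap gain in precision and robustness if left and right folds respond differently

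*Combined protocol and SAP*

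**What the plan says.** The Design row of the synopsis describes a randomised comparison that is "within-subjects: each subject testing both devices", with "55 subjects randomized" at one site. Inclusion requires a WSRS "score of 3 or 4 on both folds at the pre-treatment evaluation". Under Study Procedures, subjects are injected with the "onal devices according to the" randomisation list.

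Under Statistical methods, the quantitative secondary criteria are to be compared by a paired t test. The sentence is broken in the available text, and what survives is "ired t test will be applied to". Testing is two-sided ("The bilateral approach will be used with a significance"), but the level is cut off. The primary analysis concerns the change "le from baseline (M6-D0bef") and is judged on an upper confidence limit. Of that description only fragments such as "CI of the (M6-D0bef) mean" can be read, so the method behind the interval, its level and its margin are not legible.

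No legible text mentions left or right, side balance, or a side term.

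**The concern.** With two folds and two products per subject, the natural thing for the list to randomise is which fold receives which product. Side is then a known design factor. If one side of the face tends to change more than the other, for whatever reason, that difference adds to the product effect in subjects given Gana V on one side and subtracts from it in the others. A plain paired t test treats this alternation as random scatter, although the list identifies it exactly.

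Two things are at stake. With balanced sides, the side effect cancels from the mean but stays in the estimated variance, so the interval is wider than the design warrants. With unequal side groups, whether from the list or from missed visits, part of the side effect also remains in the estimate itself.

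**Working it through.** The synopsis states no SD, margin, power or side effect, so there is no figure of its own to reproduce.

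**Inputs**
- n = 55 paired differences (Planned Sample Size row, before any dropout).
- Two-sided 95% level: assumed, since the level is not legible.
- Side splits 28/27 (as even as 55 allows) and 33/22 (illustrative): assumed.
- lambda, half the gap in mean fold difference between the two side-allocation groups (that is, the mean left-right difference in change): not given, so a range is shown in units of sigma, the SD of the fold difference within a side group.

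**Model.** For subject i the fold difference in change, Gana V minus Sculptra, is D_i = delta + s_i × lambda + e_i. Here s_i is +1 or -1 by allocated side and e_i has SD sigma.

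**Plain paired interval.** Expected variance estimate = sigma² + lambda² × 4 n1 n2 / [n(n-1)], with 54 df and t = 2.0049. The multiplier of lambda² is 4×28×27/(55×54) = 1.018 for 28/27 and 4×33×22/(55×54) = 0.978 for 33/22.

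**Side-adjusted interval.** The estimate is the average of the two side-group means. SE = sigma × √[(1/n1 + 1/n2)/4], with 53 df and t = 2.0057.
- 28/27: SE = 0.1349 sigma, half-width 0.2705 sigma.
- 33/22: SE = 0.1376 sigma, half-width 0.2760 sigma.

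**Worked case, 28/27, lambda = 0.5 sigma.** Variance = 1 + 0.25 × 1.018 = 1.2545. Half-width = 2.0049 × √(1.2545/55) = 0.3028. Ratio = 0.3028/0.2705 = 1.119.

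| Split | lambda/sigma | Plain half-width | Plain / adjusted | Shift in plain estimate | Plain coverage |
|---|---|---|---|---|---|
| 28/27 | 0 | 0.2703 | 0.999 | 0 | 95.0% |
| 28/27 | 0.1 | 0.2717 | 1.004 | 0.002 | 95.1% |
| 28/27 | 0.2 | 0.2758 | 1.020 | 0.004 | 95.4% |
| 28/27 | 0.3 | 0.2825 | 1.044 | 0.005 | 95.9% |
| 28/27 | 0.5 | 0.3028 | 1.119 | 0.009 | 97.1% |
| 33/22 | 0 | 0.2703 | 0.979 | 0 | 95.0% |
| 33/22 | 0.2 | 0.2756 | 0.998 | 0.040 | 94.5% |
| 33/22 | 0.3 | 0.2820 | 1.022 | 0.060 | 93.9% |
| 33/22 | 0.5 | 0.3016 | 1.093 | 0.100 | 92.5% |

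Half-widths and shifts are in units of sigma. The shift is lambda × (n1 - n2)/n, which is 0.2 × lambda at 33/22. Coverage is conditional on the split, assumes normal e_i, and was obtained by integrating over the noncentral chi-squared distribution of the residual sum of squares. The adjusted interval has 95% coverage throughout.

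**Power.** In simulation (40,000 trials, 28/27), take a true difference set for nominal 80% power, (1.96 + 0.84)/√55 = 0.378 sigma. The plain test then has 77.9% power at lambda = 0.25 sigma and 73.3% at 0.5 sigma, against about 79% with the side term.

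**Break-even.** At 28/27 the side term narrows the interval once lambda exceeds about 0.034 sigma. At 33/22 it does so only above about 0.2 sigma, although it removes the shift at any lambda.

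**The case against.** The strongest reply is that nothing in the documents points to a side effect. The endpoints are changes from baseline, so a fixed facial asymmetry cancels and only a left-right difference in the response itself counts. The 12% figure needs such a difference to reach half the SD of the fold difference. Up to 0.25 SD the loss in width is about 3% or less. The paired t test is standard for this design, and with balanced sides it does not inflate type I error. All of this stands, and it keeps the point minor.

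Three stronger readings are tempting, and the documents do not support them:

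- *The plan ignores side and its intervals are too wide.* The source is a synopsis with a broken sentence. All one can say is that no side term is visible, and excess width requires a non-zero lambda. Side randomisation is itself a fair inference from the design, not something the legible text states.
- *The primary M6 comparison loses power.* The legible paired t test belongs to the secondary criteria. How the primary interval is built cannot be read, so the loss cannot be carried over to it.
- *An uneven split biases the trial.* The 33/22 split is hypothetical. If it arose by chance under simple randomisation, the shift belongs to that one allocation and averages out over the randomisation.

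Nor is adjustment always nearly free. The very small cost holds for near-even sides; at 33/22 with no side effect the adjusted interval is about 2% wider.

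**Conclusion.** The point holds as a minor matter of precision and robustness for the quantitative secondary endpoints. The loss is negligible if left and right folds respond alike and becomes material only as lambda approaches 0.5 SD of the fold difference. At that value, a 28/27 split gives the width that about 69 subjects would be needed to match without adjustment (55 × 1.25 = 68.75). At 0.2 and 0.3 SD the equivalents are about 57 and 60.

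With balanced sides the planned test is valid and errs on the cautious side. With clearly uneven sides, coverage for that allocation can fall below 95%, for example to 92.5% at 33/22 and lambda = 0.5 SD. The conclusion assumes that side is what the list randomises, a 95% level, roughly normal differences, and that the unreadable part of the sentence contains no side term.

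**What to change.** For each quantitative endpoint, pre-specify a linear model of the within-subject fold difference in change (Gana V minus Sculptra) with an intercept and allocated side coded +1/-1. Report the intercept, which is the product effect, with its confidence interval, and show the side coefficient. State whether the randomisation list is balanced by side. Apply the same model to the M6 primary interval only if that interval is a plain paired one. If the sponsor prefers to keep the paired t test as the main analysis, specify this model as a sensitivity analysis.

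The cost is one sentence in the analysis plan and one degree of freedom (54 to 53); if side is what was randomised, the list already records it. If there is no side effect, the lost degree of freedom alone widens the interval by about 0.04% (2.0057/2.0049). The total at 28/27 is about 0.06%, and at 33/22 about 2% (0.2760/0.2703 = 1.021). The choice should be fixed before unblinding, since adding side after the data are seen would invite challenge.

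### A repeated-measures model would serve the quantitative secondary endpoints better than separate paired t tests: it uses all post-treatment visits and guards against bias at M9–M24 if loss depends on the fold difference already observed

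*Combined protocol and SAP*

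**What the plan says.** The Design row of the synopsis describes a randomised split-face comparison ("within-subjects: each subject testing both devices"), and the Planned Sample Size row gives "55 subjects randomized". The flow-chart schedules WSRS scoring and fringe projection of two areas at seven post-treatment visits, from M1½ to M24.

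The Objectives and Endpoints rows list the quantitative secondary endpoints visit by visit. WSRS change is secondary at M1½ and at "3, 9, 12, 18 and 24 months after treatment initiation", with M6 reserved for the primary endpoint. Effectiveness "in reducing NLFs depth and volume" is an objective at all seven visits, and the matching endpoint also runs to M24 ("9, 12, 18 and 24 months at").

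Under Statistical methods, the secondary quantitative data get a paired t test ("ired t test will be applied to") and the qualitative data McNemar's test ("For qualitative data a McNemar's test will be applied t"). Testing is two-sided ("The bilateral approach will be used with a significance"; the level itself is cut off). The text supplied shows no repeated-measures model, missing-data rule, secondary analysis set, expected dropout or sensitivity analysis.

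**The concern.** A paired t test on change at, say, M18 needs both folds at M18 and at baseline. It ignores what the same subject showed at M1½ to M12. A subject who left after M12 contributes nothing at M18, although the fold difference was recorded at up to five earlier post-treatment visits.

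Losing both folds together keeps the two devices' counts equal, but it does not protect the contrast. The analysed quantity is the within-subject fold difference. If staying in the trial depends on that difference, those who remain are a selected sample of it. In a split-face trial over 24 months this is plausible: subjects see both results on one face, and the only scheduled touch-up is at M1½. The documents do not say that it happens.

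At stake are the late device differences, which the Objectives carry to M24, and some precision at those visits.

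**Working it through.** **Inputs from the documents.** 55 subjects, each with two folds; seven post-treatment visits; two-sided paired testing.

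**Inputs assumed, because the documents give none.** True fold difference μ = 0.3 grade; SD of the difference σ = 0.7; between-visit correlation ρ = 0.5 or 0.7; dropout after M6 of 15% or 25%; dropout risk four times higher after a large observed difference, with large taken as more than 0.7 grade.

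**The plan's own figure.** The 55 cannot be reproduced, since no effect, SD or power is visible. Inverted with an assumed two-sided 0.05 and 80% power, 55 pairs detect (1.960 + 0.842)/√55 = 0.378 SDs of the fold difference.

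**Why selection carries forward.** Let E be an earlier observed difference and L the M24 difference, with equal mean and SD and correlation ρ. If leaving depends only on E, then

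bias of the completer mean at M24 = ρ × (mean of E among stayers − μ).

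A likelihood model predicts L from E for everyone, including leavers, and so removes this term.

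**One-step hand check, absolute asymmetry, 25% dropout.**
- Share with |E| > 0.7: P(Z > 0.571) + P(Z < −1.429) = 0.284 + 0.077 = 0.360.
- Base risk p: p × (1 + 3 × 0.360) = 0.25, so p = 0.120, and 4p = 0.480 for the asymmetric group.
- Contribution of that group to the mean of E: 0.245. Contribution of leavers: 0.120 × (0.300 − 0.245) + 0.480 × 0.245 = 0.124.
- Mean of E among stayers: (0.300 − 0.124)/0.75 = 0.234, a shift of −0.066.
- Bias at M24: −0.033 for ρ = 0.5 and −0.046 for ρ = 0.7. The same steps at 15% dropout give −0.017 and −0.024.

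**Simulation with dropout spread over the visits after M6**, same inputs:

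| Who leaves | Completer bias at M24 (grade) |
|---|---|
| Large absolute difference | −0.016 to −0.041 |
| Large difference in the direction of the true effect | −0.03 to −0.08 |
| Difference below zero (mirror case) | +0.03 to +0.08 |
| Large absolute difference, true difference zero | none |
| Random | none |

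Where loss follows the last observed absolute difference, the likelihood estimate is close to unbiased. Under random loss at 25% with n = 55 its SE is 5–8% smaller. Against the true 0.3, the absolute-asymmetry bias is about 5–14% (0.016/0.3 to 0.041/0.3), and the one-signed extreme about 27% (0.08/0.3).

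**Scale against noise.** With 47 or 41 completers the SE is 0.7/√47 = 0.102 or 0.7/√41 = 0.109. The absolute-asymmetry bias is therefore about 0.16 to 0.37 of an SE.

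**Second set of assumptions** (true difference 0.40 SD, correlation 0.5–0.8, exchangeable or autoregressive, dropout log-odds 1 or 2 per SD of the previous absolute difference):

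| Dropout | Observed-case estimate | All-visit likelihood |
|---|---|---|
| 10% | 0.33–0.38 | 0.40 |
| 20% | 0.28–0.36 | 0.40 |
| 30% | 0.24–0.34 | 0.40 |

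At 20% dropout and n = 55, paired-t power is 0.53–0.65, against 0.71–0.72 with random loss. With a zero true difference and loss driven by the signed difference, false rejection at 20% dropout is 0.10–0.19. If loss depends on the current, unrecorded asymmetry, the model corrects only partly: 0.37–0.40, against 0.30–0.38 for observed cases.

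**The case against.** Several stronger readings are tempting and should be set aside.

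- **That the plan analyses only those who attend.** No sentence says so. The relevant line is truncated and the file is a six-page synopsis; a fuller document may hold a missing-data rule. What can be said is that none is visible, and that a paired t test by its nature uses one post-baseline visit.
- **That bias always runs toward no difference.** The mirror case moves the estimate away from zero, and with a zero true difference signed loss can create a spurious one.
- **That late non-significance would be read as comparability.** The visible confidence-bound rule concerns the M6 change only. No rule for M9–M24 turns a non-significant secondary test into a claim.
- **That all earlier data are discarded.** Change scores keep baseline; only the other post-baseline visits go unused.

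Other objections carry weight. Every input that drives the size is assumed. The absolute-asymmetry bias is well under half an SE. The model's near-zero bias follows from making dropout depend on an observed difference. M12, M18 and M24 are about six months apart, so the asymmetry that prompts exit may never be recorded. A subject who has one side corrected elsewhere but stays in the trial is a different problem, which this model does not solve. Unstructured covariance over seven visits needs 7 × 8/2 = 28 parameters from 55 subjects.

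These points limit the size and certainty of the gain. They do not remove it: the model uses data already collected, is no worse under random loss and is better under loss that follows observed asymmetry.

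**Conclusion.** The point holds as an inexpensive improvement to the secondary analyses, chiefly at M9–M24. The paired t test remains valid under random loss, where the model offers only modest precision. Under loss that depends on the observed fold difference, the paired estimate is biased in a direction set by the dropout mechanism, by roughly 0.02 to 0.04 grade for absolute asymmetry and up to 0.08 either way for one-signed loss. Those sizes rest wholly on the assumed difference, SD, correlation, dropout and fourfold risk. A reader might infer that the M6 primary result is also compromised; the simulated loss occurs after M6 and gives no support for that.

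**What to change.** For each quantitative secondary endpoint (WSRS change, fold depth, fold volume), pre-specify one repeated-measures model of the within-subject difference in change, Gana V minus Sculptra, at all post-treatment visits. Use visit as a fixed effect, unstructured within-subject covariance with a named simpler fallback if it fails to converge, and Kenward-Roger degrees of freedom. Report each visit's difference with its 95% CI, and keep the paired t test as a sensitivity analysis.

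State the analysis set and missing-data rule if the full plan does not already do so. Because the model corrects only partly when loss depends on unrecorded asymmetry, tabulate dropout by visit against the last observed fold difference, and add a simple missing-not-at-random sensitivity analysis, for example shifting the imputed differences of leavers in each direction.

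The cost is SAP wording, a little programming and the choice of a fallback covariance for 55 subjects. No new data are needed, and with complete data the visit means equal the paired means. The M6 primary analysis need not change.
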